3.3.4 Withdrawal of patients from therapy or assessments

Patients may potentially be withdrawn from trial treatment or from the trial as a whole ("withdrawal of consent") with very different implications, please see Section 3.3.4.1 and Section 3.3.4.2 below.

Every effort should be made to keep the patients in the trial, at least to collect important trial data.

Measures to control the withdrawal rate include careful patient selection, appropriate explanation of the trial requirements and procedures prior to randomization, as well as the explanation of the consequences of withdrawal.

The decision to withdraw from trial treatment or from the whole trial as well as the reason must be documented in the patient files and Electronic Case Report Form (eCRF).

3.3.4.1 Withdrawal from trial treatment

An individual patient is to be withdrawn from trial treatment if:

- The patient wants to withdraw from trial treatment, without the need to justify the decision.
- The patient needs to take concomitant drugs that interfere with the investigational product or other trial medication. Please refer to Section 4.2.2 for restricted medication during this trial.
- The patient requires additional medical therapy or dose increase in patient's baseline medication, as deemed by the investigator, to treat the underlying UC due to disease worsening.
- The patient can no longer be treated with trial medication for other medical reasons such as surgery, AEs, other diseases, or pregnancy.
- The patient has repeatedly shown to be non-compliant with important trial procedures and, in the opinion of both, the investigator and sponsor representative, is not willing or able to stick to the trial requirements in the future.

Exclusion criteria occurring after randomization will not necessarily be a reason for withdrawal of a patient.

Given the patient's agreement, the patient will undergo the procedures for early treatment discontinuation and follow up as outlined in the Flow Chart and Section 6.2.3.

For all patients, the reason for withdrawal from treatment (e.g., adverse event) must be recorded in the eCRF. These data will be included in the trial database and reported.

3.3.4.2 Withdrawal of consent for trial participation

Patients may withdraw their consent for trial participation at any time without the need to justify the decision. This will however mean that no further information may be collected for the purpose of the trial and negative implications for the scientific value may be the consequence. Furthermore it may mean that further patient follow up on safety cannot occur.

Boehringer Ingelheim		03 Apr 2019
BI Trial No.: 1368-0004		
c10710598-04	Trial Protocol	Page 29 of 82

If a patient wants to withdraw consent, the investigator should explain the difference between treatment withdrawal and withdrawal of consent for trial participation.

3.3.4.3 Discontinuation of the trial by the sponsor

BI reserves the right to discontinue the trial overall or at a particular trial site at any time for the following reasons:

- 1. Failure to meet expected enrolment goals overall or at a particular trial site
- 2. Emergence of any efficacy/safety information invalidating the earlier positive benefit risk-assessment that could significantly affect the continuation of the trial
- 3. Violation of GCP, the trial protocol, or the contract impairing the appropriate conduct of the trial

The investigator / the trial site will be reimbursed for reasonable expenses incurred in case of trial termination (except in case of the third reason).

03 Apr 2019

Trial Protocol

Page 30 of 82

Proprietary confidential information © 2019 Boehringer Ingelheim International GmbH or one or more of its affiliated companies

4. **TREATMENTS**

4.1 INVESTIGATIONAL TREATMENTS

Multiple doses of BI 655130 will be administered intravenously. BI 655130 will be supplied by BI.

4.1.1 Identity of the Investigational Medicinal Products

Table 4.1.1: 1	Description of test product BI 655130 12 weeks
----------------	------------------------------------------------

Substance:	BI 655130
Pharmaceutical formulation:	Solution for infusion
Source:	Boehringer Ingelheim Pharma GmbH & Co. KG, Germany
Chemical form:	Anti-human IL-36 Receptor mAb
Molecular weight:	146 kDa
Unit strength:	150mg/vial (20mg/mL)
Posology	1200mg at Day 1, at Week 4 and at Week 8
Route of administration:	intravenous infusions
Duration of Use	12 weeks

4.1.2 Selection of doses in the trial

The aim of this small exploratory study is to provide the highest likelihood to study the mechanism of BI 655130 in UC analysing various BMs in sequential biopsies. Based on other effective anti-cytokine drugs in IBD and pre-clinical assays for IL36 inhibition, a linear or logistic rather than a bell-shaped dose-response curve is expected for these BMs. Thus, the highest tolerated dose should provide the highest likelihood to achieve this objective. This dose is also expected to provide the best chance to induce clinical remissions in UC patients.

The fixed rather than weight-based dose regimen of 1200mg given at weeks 0, 4 and 8 has been selected for the following reasons:

- Early trials of therapeutic monoclonal antibodies often investigate body weight based regimens to reduce the inter-subject variability in drug exposure. However, there is generally only modest contribution of body weight to overall PK and PD variability of monoclonal antibodies. Furthermore, monoclonal antibodies are highly target-specific and offer a relatively large therapeutic window as compared to new chemical entities. Therefore, most monoclonal antibodies are approved at fixed doses in antibody/target excess in order to cover target turnover and maximize efficacy. (R13-4749, R10-6267, R13-4753, R13-4750, R13-4754).
- Body weight has been included in the current PK model as a covariate indicating decreased exposure with increasing body weight. The current model indicates that body weight explains less than 15% of between-subject variability in PK of BI 655130 when comparing a model with and without body-weight as a covariate of exposure.
- A fixed dose regimen will minimize the potential for dosing errors due to less complex dose calculation, study drug preparation and administration as compared with weight based dosing. It will also facilitate dose finding and PK-PD analyses due to covering a wider weight/exposure range (R10-6267).
- This dose regimen is the highest covered by current healthy volunteer PK and safety data irrespective of body weight.

Currently approved or investigational biologics (e.g. TNFi, vedolizumab, ustekinumab) have established 4-8 weeks duration of induction treatment in UC; a longer induction period of 12 weeks was selected to allow assessment of the response kinetics for BI 655130, which represents a new and clinically non-validated mode-of-action (MoA). The dosing interval of once every 4 weeks is supported by the long half-life of BI 655130 of approximately four weeks. The discontinuation of BI 655130 treatment after 12 weeks is supported by preclinical GLP toxicology studies with the surrogate antibody and will allow study of the PK and PD wash-out profile (clinical effect and BM) of BI 655130.

4.1.3 Method of assigning patients to treatment groups

There is only one treatment group in this trial.

4.1.4 Drug assignment and administration of doses for each patient

In this trial, a dose of 1200mg of BI 655130 will be administered intravenously at Day 1, Week 4 and Week 8. The concentration of the application solution in the infusion bag will be 20mg/mL.

Detailed instructions for the preparation of the infusion solution, the volume to be administered and the infusion rate are provided in Section 4 of the ISF.

In case of safety concerns, e.g., due to infusion reactions, it is at the discretion of the investigator or his/her designee to adapt the infusion scheme, including but not limited to slowing down the infusion rate, stopping of the infusion and provided no further safety

Boehringer Ingelheim		03 Apr 2019
BI Trial No.: 1368-0004		_
c10710598-04	Trial Protocol	Page 32 of 82

concern exists restarting at a slower rate. In any case, the total duration of infusion should not exceed 240 minutes (4 hours) provided that the maximum time between the start of preparation and completion of administration of the solution to the patient does not exceed 300 minutes (5 hours). For further instructions on how to proceed in case of an infusion reaction, please refer to Section 4.2.1.

4.1.5 Blinding and procedures for unblinding

4.1.5.1 Blinding

This is an open-label, single-arm trial. Therefore, no blinding will be necessary.

4.1.5.2 Unblinding and breaking the code

Not applicable.

4.1.6 Packaging, labelling, and re-supply

The investigational products will be provided by BI or a designated CRO. They will be packaged and labelled in accordance with the principles of Good Manufacturing Practice (GMP).

For details of packaging and the description of the label, refer to Section 4 of the ISF.

4.1.7 Storage conditions

Drug supplies will be kept in their original packaging and in a secure limited access storage area according to the recommended storage conditions on the medication label. A temperature log must be maintained for documentation.

If the storage conditions are found to be outside the specified range, the sponsor must be contacted immediately. Refer to the Section 4 of the ISF for contact information.

For further user information and in-use stability, refer to Section 4 of the ISF.

4.1.8 Drug accountability

The Investigator and/or Pharmacist and/or investigational drug storage manager will receive the investigational drugs delivered by the sponsor when the following requirements are fulfilled:

- Approval of the trial protocol by the ethics committee
- Availability of a signed and dated clinical trial contract between the sponsor and the head of the investigational site,
- Approval/notification of the regulatory authority, e.g. competent authority,
- Availability of the curriculum vitae of the principal Investigator,
- Availability of a signed and dated clinical trial protocol (CTP)

Boehringer Ingelheim		03 Apr 2019
BI Trial No.: 1368-0004		_
c10710598-04	Trial Protocol	Page 33 of 82

Only authorised personnel as documented in the form "Trial Staff List" may dispense medication to trial subjects. The trial medication must be administered in the manner specified in the CTP. The Investigator and/or Pharmacist and/or investigational drug storage manager must maintain records of the product's delivery to the trial site, the inventory at the site, the use by each patient, and the return to the sponsor or warehouse / drug distribution centre or alternative disposal of unused products. If applicable, the sponsor or warehouse / drug distribution centre will maintain records of the disposal.

These records will include dates, quantities, batch / serial numbers, expiry ('use- by') dates and the unique code numbers assigned to trial patients. The Investigator / Pharmacist / investigational drug storage manager will maintain records that document adequately that the patients were provided the doses specified by the CTP and reconcile all investigational products received from the sponsor. At the time of return to the sponsor< and/or >appointed CRO, the Investigator / Pharmacist / investigational drug storage manager must verify that all unused or partially used drug supplies have been returned by the clinical trial staff and that no remaining supplies are in the Investigator's possession.

4.2 OTHER TREATMENTS, EMERGENCY PROCEDURES, RESTRICTIONS

4.2.1 Other treatments and emergency procedures

Patients in this trial are required to be on conventional, non-biologic treatment for UC.

Conventional treatment may consist of one or more of the following drugs (cf. Section 3.3.2, inclusion criteria), which are therefore permitted concomitant medications:

- Oral 5-ASA compound, with stable dose for at least 4 weeks prior to screening and throughout the trial
- 6-MP, MTX or AZA, with stable dose for at least 8 weeks prior to screening and throughout the trial
- Oral corticosteroids (≤ 20mg/day per day of prednisone or equivalent), with stable dose for at least 4 weeks prior to screening and throughout the trial. For equivalent doses of corticosteroids, please cf. Appendix 10.3.

Dose has to be stable throughout the trial. In the event that a patient experiences an intolerable increase of UC, as deemed by the investigator, during the course of the trial, the decision whether or not to discontinue treatment (if applicable) and start rescue treatment should be taken in the discretion of the investigator and in discussion with the CML. Rescue treatment may be any new medication or any increase in dose of a baseline medication.

Stable doses of concomitant therapies for chronic conditions, for which neither the condition nor the treatment are judged to exclude the patient from participation (cf. Section 3.3.3) are permissible. All concomitant medications should be carefully evaluated by the investigator, and the CML should be contacted when there are questions regarding concomitant medications.

Details of all concomitant medication will be recorded in the eCRF, along with the main reason for prescription. In addition, all prior treatment for UC within 12 months of Visit 1a will be recorded.

Infusion reactions including anaphylactic reactions:

In case of infusion reactions including anaphylactic reactions emerging during or after infusion of BI 655130, the investigator should consider in accordance with severity of the reaction and local standard of care to

- Immediately interrupt the infusion
- Treat with systemic anti-histamines and i.v. steroids and in case of a severe allergic reaction (eg, anaphylactic reaction) epinephrine

Also draw a plasma sample for IgE and ADA as detailed in the Lab Manual (Section 10 of the ISF).

Based on patient's clinical course and medical judgment, the infusion may be re-initiated in case of mild or moderate infusion reactions (according to RCTC grading in Section 5 of the ISF) at lower speed with gradual increase to complete the infusion as detailed in the Instructions for Preparation and Handling of BI 655130 in the Investigator Site File.

In any case, the total duration of infusion should not exceed 240 minutes (4 hours) provided that the maximum time between the start of preparation and completion of administration of the solution to the patient does not exceed 300 minutes (5 hours).

In case of anaphylactic reaction, the investigator should discontinue treatment with BI 655130.

Cytokine release syndrome (CRS)

This syndrome manifests when a large number of immune cells becomes activated and releases inflammatory cytokines. It is clinically characterized by fever, chills, rigor and rash, possibly with nausea, dyspnoea, tachycardia and hypotension.

Potentially life-threatening complications of a cytokine release syndrome include cardiac dysfunction, respiratory distress syndrome, neurologic toxicity, renal and/or hepatic failure, and disseminated intravascular coagulation. In case of suspicion of a cytokine release syndrome, it is recommended to measure IL-6 levels in the local laboratory if the assay is available.

The investigator should discontinue treatment with BI 655130. Aggressive supportive care is essential for patients experiencing CRS, with early intervention for hypotension and treatment of concurrent infections. IL-6 receptor blockade with tocilizumab remains the mainstay pharmacologic therapy for CRS, though indications for administration vary among centres. Corticosteroids should be reserved for neurologic toxicities and CRS not responsive to tocilizumab (R16-5751).

0710598-04Trial ProtocolPage 35 of 82Proprietary confidential information © 2019 Boehringer Ingelheim International GmbH or one or more of its affiliated companies

Opportunistic infections or mycobacterium tuberculosis infections or serious infections

The investigator should discontinue treatment with BI 655130. Treatment of the infection has to be initiated according to local standard of care.

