The patient set for the primary evaluation of gene expression will include all patients who completed trial medication and trial through EoT visit and who provide at least one evaluable baseline and one evaluable post-baseline biopsy RNA measurement. The patient set for the safety analyses will include all patients who received at least one dose during the trial. Details on the analysis sets and further analysis sets e.g. for the BM assessments, will be defined in the TSAP.

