Categ Code		Description	Comments	Excluded from ¹	
D2		Prohibited medication use			
	D2.01	Use of restricted medication as per CTP Table 4.2.2: 1 on or after Screening or during the on-treatment period when not provided as a rescue treatment to stabilize a worsening disease condition- prior to or up to Week 12	If restricted medication is initiated during trial	CAS	#
		LABEL: Restricted medication prior to week 12			
	D2.02	Use of restricted medication as per CTP Table 4.2.2: 1 when not provided as a rescue treatment to stabilize a worsening disease condition – after Week 12	If restricted medication is initiated during trial	None	#
		LABEL: Restricted medication after week 12			
D3		Change in background medication			
	D3.01	Concurrent UC treatments need to be on stable doses during treatment:	Medical review	CAS	#
		Any dose change in background medication on or after Screening or during the on- treatment period unless it is due to rescue use or adverse event– prior to or up to Week 12			
		LABEL: Concurrent UC treatment not stable prior to Week 12			
	D3.02	Any dose change in background medication period unless it is due to rescue use or adverse event – after Week 12		None	#
		LABEL:			
		Concurrent UC treatment not stable after Week 12	Medical review		

Important protocol deviations (continued) Table 6.2: 1

PV will be detected manually

Source: BI reference document: "Identify and Manage Important Protocol Deviations (iPD)" [001-MCS-40-413] (2) ¹ See Section 6.3 for population definitions

TSAP for BI Trial No: 1368-0004 Page 23 of 48 Proprietary confidential information © 2019 Boehringer Ingelheim International GmbH or one or more of its affiliated companies

	egory /		~	-	
Cod	e	Description	Comments	Excluded from ¹	
Ε		Missing data None	Missing visits, evaluations, and tests will be considered missing data, not protocol deviations		
F		Study specific analysis			
F1		Other trial specific violation			
	F1.01	Incomplete diagnosis of ulcerative colitis	Medical review	CAS	#
		LABEL: Incomplete diagnosis of UC			
F2		Certain violations of procedures used to measure primary or secondary efficacy/biomarker data			
	F2.01	To be defined at the RPM, if applicable	Manual iPDs which have a potentially relevant effect on primary or secondary data	Any exclusion will be defined at the RPM/ DBLM/ MQRM.	#
G		Other safety related violations			
	G1	Pregnancy test not done for woman of child bearing potential		None	
		LABEL: Pregnancy test not done			

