6.6.2 Efficacy data

For the Mayo and RHI total scores, a missing item or component score will lead to a missing total score. However, individual items and subscores may be presented as applicable. It is not planned to impute missing data for any efficacy endpoint in this trial. Cf. Section 9.1 for details regarding the derivation of (clinical) efficacy endpoints.

Data censoring for rescue medication use

Rescue medication use will be identified on the eCRF. For the purpose of data censoring, the following scenarios are considered rescue therapy in this trial:

- Any medication taken (even single use) after first dose of BI 655130 and on or before end of the on-treatment period which is considered by the investigator to be rescue treatment (as per tick in the CRF);
- Any increase in the dose of background medication for UC after first dose of BI 655130 and on or before end of the on-treatment period (i.e. Treatment phase plus REP) which is considered by the investigator to be rescue treatment (as per tick in the CRF)

The following approach will be used to present the efficacy data:

• Observed cases (OC) approach will include all collected data (based on time windows as described in Section 6.7), with no imputation performed on the missing data. Such an OC approach will exclude all values measured after intake of a rescue medication (i.e. such values will be set to missing).

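### Protocol 3.3.4.1 and 4.2.1 give inconsistent rules on stopping study drug when UC worsens, and the reading applied decides whether a patient rescued before the Week 8 dose counts in the primary set

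*Protocol*

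**What the plan says.** **Withdrawal rule (protocol 3.3.4.1).** The list opens with "An individual patient is to be withdrawn from trial treatment if". One of its conditions is "The patient requires additional medical therapy or dose increase in patient's baseline medication, as deemed by the investigator, to treat the underlying UC", where the cause is disease worsening.

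**Rescue rule (protocol 4.2.1).** When UC increases to an intolerable degree, "the decision whether or not to discontinue treatment (if applicable) and start rescue treatment should be taken in the discretion of the investigator", in discussion with the local clinical monitor. The same paragraph adds: "Rescue treatment may be any new medication or any increase in dose of a baseline medication".

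**Primary set.** Protocol 7.3 states: "The patient set for the primary evaluation of gene expression will include all patients who completed trial medication and trial through EoT visit". The completers analysis set (CAS) in SAP 6.3 carries the same requirement and is the main set for the primary endpoint. Its only explicit rescue exclusion concerns rescue between Visit 1b and the first dose.

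**Rescue in the SAP.** In SAP 6.2, a background dose change up to Week 12 (code D3.01) is a deviation that excludes from the CAS "unless it is due to rescue use or adverse event". Code D2.01 makes a similar exception for restricted medication given as rescue. SAP 6.6.2 sets later data to missing: "Such an OC approach will exclude all values measured after intake of a rescue medication". SAP 6.6.6 applies this to the RNA sequencing data.

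**Replacement.** Protocol 7.7 allows up to 4 replacements for patients who leave treatment before Week 12.

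**The concern.** Both protocol sections are current text and describe the same event: worsening UC treated with a new drug or a higher dose of a baseline drug. One says study drug stops. The other leaves stopping open. A site following either section complies with the protocol.

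This reaches the analysis because the primary set is restricted to completers. A patient whose drug is stopped before the Week 8 dose has not completed trial medication and leaves the CAS, along with biopsies taken before any rescue. A similar patient kept on drug at another site can stay in the CAS and contribute those biopsies. The first patient may also be replaced and the second may not. The patients affected are those who worsened, so the inconsistency is related to outcome.

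**Working it through.** No figure in the plan can be reproduced here. The 10 patients rest on feasibility, with no power, effect size or variance behind them (protocol 7.7). The check is a comparison of texts, followed by an illustration on assumed rates.

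**1. Is it the same event?** The condition in 3.3.4.1 is added therapy or a higher baseline dose for worsening UC. The definition of rescue in 4.2.1 covers any new drug or any higher baseline dose, in the context of worsening UC. The triggers coincide. In 3.3.4.1 the investigator judges whether therapy is needed, and the consequence is then fixed. In 4.2.1 the consequence is itself open.

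**2. When can membership change?** Doses are given at Day 1, Week 4 and Week 8. After the Week 8 dose all trial medication has been given, so stopping no longer affects that part of the completer definition. The relevant window is after the first dose and before the Week 8 dose.

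**3. Which samples are at stake?** SAP 7.4 reports five time points: V2 (4 hours post-dose), V3 (Day 4), V4 (Week 2), V7 (Week 8) and EoT. For a patient rescued in that window who meets the other CAS conditions:

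| Sample | Drug stopped (3.3.4.1) | Drug continued (4.2.1) |
|---|---|---|
| Baseline | not in CAS | in CAS |
| V2, 4 h | not in CAS | in CAS |
| V3, Day 4 | not in CAS | in CAS if taken before rescue |
| V4, Week 2 | not in CAS | in CAS if taken before rescue |
| V7, Week 8 | not in CAS | normally set to missing as post-rescue |
| EoT | not in CAS | set to missing as post-rescue |

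At V7 the biopsy precedes the infusion (protocol 6.2.2), so rescue before that dose will normally also precede the biopsy. The number of patients contributing at V7 and EoT is therefore normally the same under either reading. Direct differences are confined to at most three of the five time points. Counts at V7 and EoT could move only indirectly, because all time points are fitted in one model.

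**4. How often might it arise?** The documents give no rescue rate. Let r be an assumed probability that a treated patient is rescued in the window, independently between patients and with no other losses.

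- At least one of 10 affected: 1 − (1 − r)^10
- Expected completers among 10 if rescue always means stopping: 10(1 − r). If all rescued patients continue, the number can stay at 10.
- At least 10 completers if all 4 replacements are used: P(X ≥ 10), with X binomial(14, 1 − r)

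| r (assumed) | At least 1 of 10 affected | Expected completers of 10 if stopped | At least 10 completers of 14 |
|---|---|---|---|
| 10% | 1 − 0.349 = 0.651 | 9 | 0.991 |
| 20% | 1 − 0.107 = 0.893 | 8 | 0.870 |
| 30% | 1 − 0.028 = 0.972 | 7 | 0.584 |
| 40% | 1 − 0.006 = 0.994 | 6 | 0.279 |

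Even at 10% the question would probably arise at least once. Replacement can largely restore the number of completers at the lower rates, but it does not bring back the early biopsies of the patient who worsened.

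**The case against.** **The sections can be harmonised.** 4.2.1 may describe one joint decision to stop drug and start rescue, with its bracketed qualifier meaning that the patient is still on treatment. That is possible, since 4.2.1 covers the whole trial, including the time after the last dose. But the text does not say so. Elsewhere 4.2.1 says plainly that the investigator should discontinue drug, as for cytokine release syndrome and serious infections. Discussion with the local clinical monitor may reduce variation between sites, but it does not supply the missing rule.

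**The SAP settles it.** A reader might infer from D2.01 and D3.01 that the SAP expects rescued patients to stay on drug. The documents do not support that. A patient rescued between the Week 8 dose and Week 12 has had every dose, so the exemptions are needed even if stopping is compulsory. The post-rescue rule also serves the full analysis set (FAS), which can hold withdrawn patients. The SAP text fits both readings.

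**The FAS covers it.** SAP Table 6.3:1 lists the primary endpoint for the FAS, which does not require completion. This helps, but SAP 7.4 places that analysis among those that may be conducted. It is a partial remedy.

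**The trial is exploratory.** No confirmatory test is planned (protocol 7.2). That limits the seriousness, but the primary count still needs a set whose membership does not depend on a site's reading of the protocol.

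**Conclusion.** The point holds, within limits. The two sections are inconsistent, and compliant sites can act differently. For a patient rescued after the first dose and before the Week 8 dose, the reading applied decides three things: completer status, whether the pre-rescue biopsies enter the primary analysis, and whether the patient may be replaced. Each such patient is 1 of 10 planned (10%).

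Two stronger conclusions are tempting and are not supported. One is that all primary counts depend on the reading: V7 and EoT samples are normally censored either way, and rescue after the Week 8 dose does not raise the issue. The other is that the gene count would fall by some stated percentage: the documents give neither a rescue rate nor the variability needed for such a figure, and up to 4 replacements may offset the loss in numbers. The rates in the illustration are assumptions.

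The change is worth making because it is cheap and removes an inconsistency related to outcome. It does not call the design into question.

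**What to change.** 1. Reconcile protocol 3.3.4.1 and 4.2.1 so that one rule applies at every site, with a cross-reference between them. Which rule is for the sponsor to decide; no view is taken here.
2. Align the SAP rescue and deviation text (6.2 and 6.6.2) and the replacement rule in protocol 7.7 with that rule. State how a rescued patient is classified for the CAS and for replacement.
3. Amend both protocol 7.3 and the CAS definition in SAP 6.3 so that evaluable samples taken before rescue stay in the primary gene-expression analysis, whether or not study drug was stopped. Changing the SAP alone would leave it in conflict with protocol 7.3.
4. At minimum, if the completers set is kept, make the FAS analysis of the primary endpoint mandatory.

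The cost is a small protocol and SAP text change, with no new data. The drawback of item 3 is that the primary set is no longer strictly completers, and the report should say so.
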